3.4 Primary Endpoint

Primary endpoint: 28-day organ support-free days, incorporating mortality.

This is a composite ordinal scale outcome. All deaths are scored "-1" on the ordinal scale, i.e., the worst outcome. Then to assess important changes in outcome for surviving participants, the number of days free of organ support up until day 28 is calculated, so that a high score is good as it corresponds to a quicker recovery. Organ support is defined as needing either respiratory or cardiovascular support. Respiratory support is defined as invasive mechanical ventilation or non-invasive ventilation including continuous positive airway pressure or high-flow nasal oxygen with an FiO2 ≥ 0.4 and a flow rate ≥30L/min. Cardiovascular support is defined as the continuous infusion of any vasopressor or inotrope medication.

Being free of organ support is defined as the last time receiving support and does not require a specified time period to define success.

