6.3 Randomisation and Blinding

The trial is open-label whereby participants, the clinical team and study team will not be masked to the interventions. To avoid bias during the ongoing PANTHER platform, where possible, modifications will be made. Only the unblinded trial statisticians will have access to emerging aggregate data and results by treatment allocation until interventions are stopped. These statisticians will be responsible for carrying out the adaptive analyses and construction of all statistical reports for regular DMC meetings.

Confidential Page 19 of 48

Each participant will be assigned a unique trial ID which is linked to their treatment allocation.

Bias will be minimised by the following:

Detection and performance: The primary outcome and most of the secondary outcomes are objective outcomes that will be unaffected by knowledge of treatment allocation. The unblinded trial statistician undertaking the planned adaptive analyses will not be involved in design decisions of the ongoing platform. Delivery of usual care based on international guidelines will decrease the likelihood of performance bias. No aggregate data by intervention will be available to the study team throughout the trial prior to any statistical trigger being met and final analysis.

Selection bias: Treatment allocation will be concealed prior to randomisation using an automated online system. To ensure clinicians have equipoise, we will evaluate screening logs and examine reasons why patients have not been enrolled into the study.

Attrition bias: The primary outcome along with most other outcome data will be collected during the hospital stay. Data on mortality will be derived electronically from routinely collected health data sources where possible. Experience from previous trials indicates missing outcome data for the primary outcome and mortality to day 90 will be minimal both in the UK and at international sites. Withdrawal rates are typically <5% in critical care trials (10,11). We will seek participants' (or their representatives'), permission to retain data collected up until the time-point that they choose to withdraw. This will maximise primary and secondary outcome data acquisition. Our experience in the UK and internationally is that patients normally agree to proceed on this basis.

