9.4 Adaptive analyses

Regular adaptive analyses will be carried out to monitor the accrued data. Participant baseline characteristics will be summarised by treatment group and overall using suitable descriptive statistics. Adaptive analysis will include formal stopping rules on the primary outcome which will be triggered by comparing the estimated treatment effect to predefined efficacy and futility boundaries. Summary and between-intervention statistics for secondary and safety outcomes will be presented by treatment group.

The first adaptive analysis will take place at the end of the calendar month when the cumulative number of participants recruited into the larger (hypoinflammatory) subphenotype reaches 240, i.e. 80 per intervention. Thereafter, adaptive analyses will take place every 3 calendar months unless recruitment varies substantially from the planned recruitment rate, in this case the frequency of the adaptive analysis will be revised. The hypoinflammatory subphenotype will be analysed at every adaptive analysis; the smaller (hyperinflammatory) subphenotype will be included in the regular adaptive analysis when its cumulative recruitment total has reached 240 participants and at alternating analyses thereafter, i.e. every 6 months, unless recruitment varies substantially from the planned recruitment rate.

When a new treatment intervention is added to the hypoinflammatory subphenotype, it will be analysed at the first adaptive analysis when it exceeds 80 recruits and at every analysis thereafter until stopping. When a new treatment intervention is added to the

Confidential Page 30 of 48

hyperinflammatory subphenotype, it will be analysed at the first analysis when it exceeds 80 recruits and at alternate analyses thereafter until stopping. The threshold of 80 recruits was chosen to maximise the potential for early stopping (and hence the efficiency of the platform) while also limiting type I error rates, which are higher in smaller samples.

Recruitment to a treatment group within a given subphenotype will be halted when an analysis reveals that an efficacy or futility boundary has been breached, or when the sample size cap is reached or at the discretion of the DMC based on wider review of the trial data. At this point, a final analysis of that treatment within subphenotype with respect to all outcomes will be carried out. After a treatment is stopped a new treatment intervention within that subphenotype may be initiated.

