At the first adaptive analysis, confirmation of the validity of the proportional odds assumption will be carried out in each subphenotype. This will be based on the observed distribution of the primary outcome ordinal scale in each treatment intervention compared to usual care. If the proportional odds assumption is not met, then alternative categorisations (i.e. grouping some categories in the ordinal scale together) will be explored. For all adaptive analysis we will examine the consistency of the unadjusted between-group treatment effect across the composite outcome elements (death and organ support free days) for each comparison within each subphenotype.

Very little missing data are expected for the primary outcome; we anticipate minimal loss to follow-up, and eCRFs will be designed so that recording of primary outcome data is mandatory. If the level of missingness does not exceed 5% then the missing data will be assumed to be ignorable, i.e. a complete case analysis will be carried out. If over 5% of outcome data are missing, then the missingness pattern and relationship to other variables will be explored and multiple imputation will be performed.

Statistical stopping triggers

The criteria for stopping recruitment to a treatment group within either subphenotype are based on the probability that the unadjusted odds ratio crosses a predefined value by a predetermined probability threshold. The initial triggers for stopping were identified through extensive simulations to optimise the trial operating characteristics and achieve an appropriate balance between the sample size needed, maximising the power to graduate treatments exceeding the minimal clinically important effect and minimising the chance of graduating treatments with no effect (type I error).

Stopping recruitment to a treatment within either subphenotype will be considered if any of the following conditions are met at any adaptive analysis:

- For efficacy if there is at least an 84% probability of the proportional odds ratio exceeding 1.1.
- For futility if there is at least a 78% probability of the proportional odds ratio falling below 1.075.

These are considered non-binding stopping rules as the DMC will also take into consideration information presented on other outcomes including safety and recruitment data.

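### Section 9.4 lets a proportional odds check on unblinded between-arm data, at about 80 per arm, reopen the primary scale and does not say that the stopping triggers stay on the full scale

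*Protocol*

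**What the plan says.** Protocol section 9.4 sets the timing of the check: "At the first adaptive analysis, confirmation of the validity of the proportional odds assumption will be carried out in each subphenotype". The data are comparative: "This will be based on the observed distribution of the primary outcome ordinal scale in each treatment intervention compared to usual care". The response to a failed check is open-ended: "If the proportional odds assumption is not met, then alternative categorisations (i.e. grouping some categories in the ordinal scale together) will be explored".

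The same section places the first analysis where hypoinflammatory recruitment "reaches 240, i.e. 80 per intervention". The hyperinflammatory stratum enters "when its cumulative recruitment total has reached 240 participants and at alternating analyses thereafter". The efficacy trigger (at least 84% probability that the proportional odds ratio, POR, exceeds 1.1) and the futility trigger (at least 78% probability that it lies below 1.075) apply at every adaptive analysis, including this one.

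Sections 3.4 and 9.5 fix the outcome without qualification. Deaths score -1, and for survivors "the number of days free of organ support up until day 28 is calculated", which gives 30 levels. The summary measure is the POR.

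Section 6.3 restricts aggregate data by allocation to the unblinded statisticians, and states: "The unblinded trial statistician undertaking the planned adaptive analyses will not be involved in design decisions of the ongoing platform". No section says who would decide on a regrouping, or whether the triggers would then be read on the full or the regrouped scale.

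**The concern.** A check on arm-versus-usual-care distributions shows the treatment effect at every cut point. Any grouping chosen afterwards can therefore depend, even unintentionally, on where the drug happens to look good. Two things are at stake.

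- **Error rates.** Section 9 quotes type I error and power for the stated triggers, derived from assumed outcome distributions and PORs. Nothing says that these figures allow for a scale chosen after the look.
- **Estimand.** If odds are truly proportional, regrouping leaves the true POR unchanged and only loses information. If they are not, the POR depends on the grouping, so a regrouped primary analysis would estimate something other than what section 9.5 defines. Different groupings in the two subphenotypes would also sit badly with the combined analysis in section 9.6, which uses the same regression model.

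Regrouping is not needed for the analysis to be usable. Without exact proportionality, the full-scale POR can still be reported as an average shift.

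**Working it through.** **Inputs from the protocol.** 240 participants over 3 arms gives 240/3 = 80 per arm. The triggers are as above. Target PORs are 1.4 (hypoinflammatory) and 1.3 (hyperinflammatory). Recruitment of 70 per month with a 70:30 split gives 70 × 0.7 × 3 / 3 = 49 per arm per 3-month look (hypoinflammatory) and 70 × 0.3 × 6 / 3 = 42 per arm per 6-month look (hyperinflammatory). The hypoinflammatory cap is 504 per intervention.

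**Assumptions, because the protocol does not print these.**
- Outcome shapes: hypoinflammatory, 21% deaths and 10-15% with 0 days; hyperinflammatory, 30-40% deaths and 12% with 0 days; the rest skewed towards high values. The 21% fits the stated mortality reduction of about 5%: odds 0.21/0.79 = 0.266, divided by 1.4 = 0.190, i.e. 16.0%.
- A vague prior (SD 10 on the log POR), since the variance of the neutral prior is not given.

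**Step 1: first look by hand.** Information on the log POR with n per arm is V = n(1 − Σp³)/6. With Σp³ = 0.02, V = 80 × 0.98/6 = 13.07 and SE = 1/√13.07 = 0.277. The efficacy trigger needs an estimate of at least ln 1.1 + 0.994 × 0.277 = 0.095 + 0.275 = 0.370. Under the null, P(Z > 0.370/0.277 = 1.34) = 9.0%. With Σp³ = 0.1, V = 12 and the result is 9.3%.

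**Step 2: reproduce the plan's figures.** Sequential simulation used looks at 80, 129, ..., 472, 504 per arm (hypoinflammatory) and 80, 122, ..., 290 (hyperinflammatory, within four years).

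| | Stated | Reproduced |
|---|---|---|
| Hypo type I error | 17-19% | 17.7-19.2% |
| Hypo power | 92-96% | 89-91% (futility acted on), 93-94.5% (ignored) |
| Hyper type I error | 18% | 17.1-17.5% |
| Hyper power | 70-71% | 68-71% |

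Type I error reproduces closely. Hypoinflammatory power comes out 1 to 3 points low. With a prior SD of 1, type I error is 16.5-18% (hypo) and about 16% (hyper).

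**Step 3: how noisy is the check at 80 per arm?** Proportional odds were made exactly true. Odds ratios were taken at five cut points (death, ≤0, ≤7, ≤14 and ≤21 days).
- Largest and smallest differ more than 1.5-fold in 56-72% of trials and more than 2-fold in 14-28%.
- The SD of log OR(death) minus log OR(≤14 days) is 0.32-0.41, about the size of the target effect, ln 1.4 = 0.34.
- A formal 5% test flags about 4.5% under exact proportionality, but only 14-30% when the truth is OR 1.0 for death and 1.4 elsewhere.

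**Step 4: type I error if a regrouped scale fed the triggers.** Hypoinflammatory, whole trial, futility ignored, two assumed shapes, 40,000 trials each (Monte Carlo SE about 0.2 points). Candidates were the full scale and five groupings, including a death/alive split.

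| Rule | Type I error | Without death/alive split |
|---|---|---|
| Full scale kept | 18.5-18.8% | – |
| One fallback fixed in advance (death/0/1-7/8-14/15-21/22-28), used if spread >2-fold | 18.6-18.7% | – |
| Random grouping if spread >2-fold | 19.2-19.7% | 18.7-19.0% |
| Most favourable, gated by formal 5% test | 19.6-19.9% | 19.2-19.6% |
| Most favourable if spread >2-fold | 22.7-25.0% | 20.5-22.3% |
| Most favourable if spread >1.5-fold | 28.9-30.8% | 24.2-26.4% |

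At the first look alone, false efficacy goes from about 9% on the full scale to 13-15% with the most favourable grouping under the 2-fold gate. For the hyperinflammatory shape, whole-trial type I error is 17.1% on the full scale, 18.1% under the 5% test gate, 20.0% under the 2-fold gate and 25.2% under the 1.5-fold gate.

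**The case against.** - **The text says explore, not replace.** This stands. A reader might infer that a failed check changes the primary endpoint and that the same triggers then run on the new scale. No section says so, and sections 3.4 and 9.5 fix the outcome. The gap is that section 9.4 does not exclude it.
- **Section 6.3 is not contradicted.** This also stands. It is tempting to read its firewall as conflicting with the check, but section 9.4 names no decision-maker. Those who can see the check may not take design decisions, and how a regrouping would be decided is left open. That is an unresolved point, not a contradiction.
- **Criteria and candidate groupings belong in the SAP.** Fair: their absence from the protocol is no fault in itself. What the protocol does fix is the use of between-arm data and an open-ended response.
- **The large inflation is a worst case.** Correct. It needs someone to pick the most favourable grouping under a 1.5-fold or 2-fold gate. Those gates are assumptions of this check and not the plan's. Section 9.6 fits one model per subphenotype, so interventions would presumably share a scale, and a grouping that favours one need not favour the other. A random pick adds at most about 1 point, and section 9 accepts around 20%.
- **A formal test would rarely raise a false alarm.** True, but section 9.4 describes looking at observed distributions, and such a test has little power at this size.
- **Other safeguards exist.** The triggers are non-binding, and consistency across death and organ support-free days is examined at every adaptive analysis. These soften the consequence but do not settle the scale.

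**Conclusion.** The point holds as a stated procedure that is fixed badly. The check uses unblinded arm comparisons at a size where it cannot separate real from chance non-proportionality, and the response to it leaves open which scale drives the triggers.

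If a grouping chosen after the look fed the triggers, hypoinflammatory type I error would go from about 18.5% to 19-20% under a formal 5% gate, and to 23-31% in the worst case. A fallback fixed in advance costs nothing measurable. These ranges rest on assumed outcome shapes, a vague prior, the candidate groupings and the recruitment projection. They are not predictions for this trial.

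The documents do not support saying that the endpoint is already data-driven, or that the quoted error rates are wrong as they stand. Severity: should be fixed before the first adaptive analysis, because after that look the choice can no longer be made blind.

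**What to change.** Amend section 9.4 to state that the full ordinal scale and its POR remain the primary estimand and the basis of all efficacy and futility triggers, whatever the proportional odds check shows. Report as supporting analyses the odds ratios at pre-specified cut points, 28-day mortality (already a secondary endpoint) and a partial proportional odds model.

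If a coarser scale might be needed, name one fallback grouping and the criterion for using it before the first look. Choose both from pooled, arm-blind or external data, apply the grouping to all interventions within a subphenotype, and say who decides.

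The cost is one paragraph of wording. The price is interpretive: if odds are not proportional, the POR is reported as an average effect and read beside the supporting results.

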9.5 Primary Estimand for Adaptive and Final Analysis

The primary estimand for the primary outcome is specified in the table below. An intercurrent event is an event that occurs after randomisation and may impact the outcome or stop us observing the outcome. Three intercurrent events have been identified: death; non-adherence; and use of other effective medications. We want to estimate the treatment effect regardless of non-adherence and use of other medications (treatment policy approach). The intercurrent event of death is handled by including it in the primary outcome definition (composite strategy).

[figure not shown]
Estimand attribute	Primary estimand			
Population	Patients meeting the inclusion criteria and no exclusion criteria			
Treatment conditions	(Active treatment + usual care) vs usual care			
Outcome variable	An ordinal outcome: composite of organ support- free days up to 28 days and death			
Population-level summary measure	Proportional odds ratio comparing each active treatment vs usual care			
Intercurrent event: strategies	Death: Composite strategy (included in the outcome) Protocol non-adherence: Treatment policy strategy Use of other effective medications: Treatment policy strategy			

9.6 Primary Modelling Approach for Adaptive and Final Analysis

'Adaptive analyses' are those performed regularly to make decisions for changing the trial. 'Final analysis' will performed once an intervention arm has met a statistical trigger and the DMC have confirmed stopping.

The primary efficacy analyses will be based on single Bayesian proportional odds logistic regression models fitted for each subphenotype. The primary **adaptive analysis** will be **unadjusted** and the **final primary efficacy** analyses will be **adjusted** for minimisation covariates and other strong prognostic variables. For adaptive and final analyses the posterior distribution of the proportional odds ratio (POR) associated with each treatment (relative to usual care) will be estimated using Markov Chain Monte Carlo techniques and the mean and 95% credible interval reported, and for the adaptive analyses the probability of exceeding the relevant statistical triggers (see above in Statistical stopping triggers). POR>1 relative to usual care indicates a favourable treatment effect. We will also examine the treatment effect across both subphenotypes by combining the data across

Confidential Page 32 of 48

subphenotypes and using the same regression model, reporting the POR and 95% credible interval. Full details of the adaptive and final analyses will be specified in the corresponding SAPs.

The primary analysis will use neutral informative prior distribution on the treatment effect where the variance will be chosen to only make extreme results highly unlikely. Where external trial evidence is available on the effect of an intervention in a particular subphenotype, a sensitivity analysis will include this evidence in the analysis using an informative prior distribution. Unadjusted and adjusted treatment effects will be presented in all reports.

Secondary efficacy endpoints

Secondary efficacy outcomes will be summarised and tabulated and unadjusted treatment effects will be calculated at each adaptive analysis. Full model-based analyses will be performed only at the final analysis for each treatment intervention in each subphenotype (i.e. once recruitment to a treatment group within a subphenotype is stopped).

Estimands for analysis of secondary efficacy endpoints will use the same treatment conditions, the same population, and intercurrent events and strategies to handle these, apart from the outcome 'Progression to invasive mechanical ventilation, extracorporeal membrane oxygenation or death' which will use the population consisting of those participants not intubated at baseline and the handling of mortality which will alter depending on the nature of the outcome and its interpretation in relation to death, and length of stay which will use the population who survived. The outcome variable and population-level summary measure will vary as appropriate for each endpoint. All secondary estimands will be specified in the SAP.

Treatment effects for final analysis will be estimated using a regression modelling approach in a Bayesian framework with vague priors. Adjustment for baseline values will be used where suitable.

Analysis of ordinal secondary outcomes (days free of vasopressor or respiratory support) will be as per the primary outcome. Analysis of binary outcomes at single time points will use logistic regression. Analysis of continuous outcomes will use linear regression.

Posterior mean contrasts (differences, odds ratios, incidence rate ratios) between treatment groups will be reported together with 95% credible intervals. Model assumptions will be examined using residual analysis including examination of graphical displays such as normal quantile plots.

Serious Adverse events

In addition to the information on safety provided by the adaptive analyses of the primary and secondary outcomes, cumulative data on SAEs will be presented to the Data Monitoring Committee on a regular basis.

As there is monitoring of important safety outcomes through primary and secondary outcomes (eg mortality, organ support), these events will not be recorded as SAEs as described above. All other SAEs will be tabulated by arm and compared between arms through calculation of incident rate ratios (IRR) and 95% credible intervals (CI).

Confidential Page 33 of 48

London

Estimands for SAEs will be based on the same treatment conditions and population as the primary estimand. Three intercurrent events have been identified: death: non-adherence: and use of other effective medications that prevent or affect the occurrence of SAEs. We will specify appropriate analytical approaches to handle these events in the analysis of SAEs in the detailed statistical analysis plan. SAEs will be summarised at the Preferred Term level and System Organ Class level and tabulated by treatment intervention.

Full analysis plan details plus supplementary and secondary estimand definitions with corresponding analysis details are specified in the statistical analysis appendices.

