3.5 Secondary Endpoints

- 28-day vasopressor-free days i.
- 28-day respiratory support-free days ii.
- lii. Receiving new renal replacement therapy
- iv. Progression to invasive mechanical ventilation, extracorporeal membrane oxygenation or death among those not receiving that support at baseline
- ICU length of stay ٧.
- vi. Hospital length of stay
- vii All-cause mortality at 28 and 90 days
- viii. Safety outcomes:-
 - Elevated Creatine Kinase more than 10 times the upper limit of normal
 - Alanine Transaminase or Aspartate Transaminase more than 8 times the upper limit of normal
 - Severe thrombocytopenia, out of keeping with clinical disease
 - Severe neutropenia, out of keeping with clinical disease
 - Serious infection defined as a positive blood cultures requiring treatment and pulmonary aspergillosis requiring treatment
 - Venous thromboembolism
 - Stroke
 - Myocardial infarction

Confidential Page 16 of 48

	Protocol No: 175151	Sponsor:	Imperial	College	V 2.1 30.07.2025
	1 1010001110. 110101	London	mpona	ooogo	7 2.1 00.07.2020
		London			
PANTHER					

- Ischaemic bowel
- Gastrointestinal perforation
- Clinically important gastrointestinal (GI) bleeding. Defined as overt bleeding on GI endoscopy, developing as a complication in the ICU and accompanied by 1 or more of the following features within 24 hours:-
 - Spontaneous drop of systolic, mean arterial pressure or diastolic blood pressure of 20mmHg or more
 - o Start of vasopressor or a 20% increase in vasopressor dose
 - Decrease in haemoglobin of at least 2 g/dl
 - o Transfusion of 2 unites of packed RBC or more
- ix. Serious adverse events
- x. Physical function (SPPB) at hospital discharge (up to 1 week prior to discharge)
- xi. Cognitive function (MoCA) at hospital discharge (up to 1 week prior to discharge)

If it is not possible to collect physical function and cognitive impairment measures prior to hospital discharge, this will not be a protocol deviation.

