- a 70: 30 ratio for hypoinflammatory: hyperinflammatory subphenotype;
- primary outcome distributions by subphenotype based on data from the HARP-2 trial (10);
- a minimally clinically important proportional odds ratios of 1.4 in the hypoinflammatory and 1.3 in the hyperinflammatory subphenotype. These were selected to yield a similar absolute reduction in mortality (~5%) over 28 days in each subphenotype

The same assumptions provide the following bounds for power and type I error rates over the initial 4-year funded period. Only upper and lower bounds can be provided (except where these coincide) since the actual operating characteristics will depend on whether the (non-binding) futility trigger is acted upon.

- A power of 92-96% in hypoinflammatory subphenotype and type I error rate (POR=1) of 17-19%.
- A power of 70-71% in the hyperinflammatory subphenotype and type I error rate (POR=1) of 18%.

A type I error rate of around 20% was judged as acceptable trade-off for enabling rapid identification of possibly effective treatments at phase II. Further precision in estimation and strength of evidence for the intervention will be gained at phase III. The total sample sizes presented are the number needed without missing data. Loss-to-follow up needs to be factored into recruitment targets.

Confidential Page 29 of 48

The sample size required for any new interventions will depend on the primary outcome distribution and anticipated effect size of the new intervention and may require further simulations.

Full details of the initial and any new sample size simulations are provided in the Statistical Design Appendix

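### ICU and hospital length of stay are to be compared among survivors, a group formed after randomisation that the drugs are meant to change

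*Protocol*

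**What the plan says.** Protocol section 3.5 lists ICU length of stay as secondary endpoint v and hospital length of stay as the next ("vi. Hospital length of stay"). Section 9.6, under secondary efficacy endpoints, lets the secondary estimands inherit the primary's population and intercurrent-event strategies, with named exceptions. One is length of stay: "and length of stay which will use the population who survived". No survival horizon is attached (28 days, 90 days or discharge), and no principal-stratum estimand or assumption is named.

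Section 9.5 gives the general framework: "An intercurrent event is an event that occurs after randomisation and may impact the outcome or stop us observing the outcome". Death comes first in the list: "Three intercurrent events have been identified: death; non-adherence; and use of other effective medications". For the primary outcome, death is absorbed by a composite strategy, so every randomised patient stays in the comparison.

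The sample size text in section 9 sets "a minimally clinically important proportional odds ratios of 1.4 in the hypoinflammatory and 1.3 in the hyperinflammatory subphenotype", and adds: "These were selected to yield a similar absolute reduction in mortality (~5%) over 28 days in each subphenotype".

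Section 9.6 leaves the full secondary estimands to the SAP, but it fixes the length-of-stay population itself.

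**The concern.** The protocol treats death as a post-randomisation event and then selects on it for two endpoints. The interventions are meant to change survival, so a drug that works as designed alters who enters the length-of-stay comparison. Its survivors include patients who would have died under usual care. If their stay differs from that of other survivors, the mean shifts even when no patient's own stay has changed.

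A useful drug could then appear to lengthen ICU or hospital stay. Equally, a drug that raises mortality could appear to shorten it by removing patients who would have stayed long. Unadjusted effects on secondary efficacy outcomes are calculated at every adaptive analysis (section 9.6), and the DMC weighs other outcomes when it considers the non-binding triggers (section 9.4). A misleading contrast could therefore be read before the final report.

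**Working it through.** The protocol gives no length-of-stay figure, standard deviation or power, so there is no stated result to reproduce. The check asks how large the artefact is at the trial's own target effects.

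**Inputs from the protocol.** Target POR 1.4 (hypoinflammatory) and 1.3 (hyperinflammatory), and a target mortality reduction of about 5 points (section 9). Section 2 cites ARDS mortality of up to 30-50%.

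**Assumptions.** Control mortality by subphenotype is not given, so p0 = 20-50% is assumed. The extra stay of saved patients over other survivors is assumed as D = 5, 10 or 20 days. The drug saves some patients, causes no deaths and changes nobody's length of stay.

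**Step 1: mortality on the drug.** Under proportional odds the POR applies to the cut between death and survival. The odds of death are o = [p0/(1-p0)]/POR, and p1 = o/(1+o). Example: p0 = 20%, POR 1.4 gives o = 0.25/1.4 = 0.1786 and p1 = 0.1786/1.1786 = 15.2%.

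**Step 2: share of treated survivors who are alive because of the drug.** f = (p0-p1)/(1-p1). Example: 0.0485/0.8485 = 0.057.

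**Step 3: artefact.** If patients who survive on either arm have mean stay μ, the control survivors' mean is μ. The treated survivors' mean is (1-f)μ + f(μ+D) = μ + fD. The apparent prolongation is f × D, although the true effect on stay is zero.

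| p0 | POR | p1 | Fall (points) | f | D = 5 | D = 10 | D = 20 |
|---|---|---|---|---|---|---|---|
| 20% | 1.4 | 15.2% | 4.85 | 0.057 | 0.29 | 0.57 | 1.14 |
| 30% | 1.4 | 23.4% | 6.56 | 0.086 | 0.43 | 0.86 | 1.71 |
| 30% | 1.3 | 24.8% | 5.21 | 0.069 | 0.35 | 0.69 | 1.38 |
| 40% | 1.3 | 33.9% | 6.10 | 0.092 | 0.46 | 0.92 | 1.85 |
| 50% | 1.3 | 43.5% | 6.52 | 0.115 | 0.58 | 1.15 | 2.31 |

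The last three columns are days. The two rows closest to the design's 5-point reduction (20% with POR 1.4, and 30% with POR 1.3) give 0.29-1.14 and 0.35-1.38 days. With D = 0 every entry is zero. With D negative the sign reverses. With POR = 1, f = 0 and there is no artefact.

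**Step 4: check of direction by simulation.** Two million patients were simulated with a shared severity factor. Log-normal stay had a median of 12 days and rose with severity; the liability to death had correlation 0.7 with severity. Each patient's stay was the same under both arms. All these inputs are assumed.

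- p0 = 20%, POR 1.4: survivors' mean stay 13.28 days (control) against 13.66 (drug), +0.39 before rounding. Alive and discharged by day 28: 74.16% against 78.05%.
- p0 = 40%, POR 1.3: 11.85 against 12.27 days, +0.42. Alive and discharged by day 28: 57.02% against 62.40%.

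The implied D is 0.39/0.057 = 6.8 days and 0.42/0.092 = 4.6 days, near the low end of the assumed range. In the same data the survivor comparison points against the drug and the all-randomised measure points in its favour.

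**The case against.** **The restriction answers a real problem.** Raw length of stay in everyone randomised is shortened by early death, so a drug that kills could look efficient. That is true, and it is a reason not to use raw stay in all patients. It does not make the survivor contrast a randomised one.

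**The SAP may add another estimand.** Sections 9.6 and its closing text leave secondary and supplementary estimands to the statistical appendices, which are not at hand. A reader might infer that survivors' stay is the only length-of-stay analysis there will be; the protocol does not establish that. It does fix the survivor population for the stated estimand, and a SAP that follows it inherits the difficulty.

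**The model is not stated for this endpoint.** Section 9.6 says "Analysis of continuous outcomes will use linear regression", and a reader might infer that this covers length of stay. The protocol never classes stay as continuous and lets the summary measure vary by endpoint. The point rests on the population, not on the model.

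**The artefact may be lost in noise.** Assume a standard deviation of 10-20 days, equal arms at the expected mean sizes in section 9 (120 and 82), and control mortality of 20% and 40%. Survivors then number 120 × 0.80 = 96 and 120 × 0.848 = 101.8, giving a standard error of SD × √(1/96 + 1/101.8) = 1.4-2.8 days. In the hyperinflammatory stratum they number 49.2 and 54.2, giving 2.0-3.9 days. The simulated 0.4 days is well below one standard error. This stands as a limit on practical impact, but a bias does not shrink as numbers grow. At the hypoinflammatory cap of 504 per arm (survivors 403.2 and 427.6) the standard error is 0.7-1.4 days.

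**Other endpoints protect the reader.** The primary outcome includes death, mortality at 28 and 90 days is reported, and the support-free-day endpoints follow the primary's model. A survival benefit would be visible beside any longer stay. This stands, and it keeps the point below the level of a threat to the trial's main conclusions.

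**Conclusion.** The point holds for two secondary endpoints. The protocol defines their population by an event after randomisation that the drugs are intended to change, without a survival horizon or the assumptions that a survivor contrast would need. The artefact is roughly 0.3-2.3 days under control mortality of 20-50% and 5-20 extra days in saved patients. Those inputs are assumptions, not protocol figures.

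Stronger readings that a reader might draw are not supported:

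- **That the bias always runs against life-saving drugs.** The direction depends on whether saved patients stay longer or less long than other survivors, and the protocol has no data on this.
- **That the survivor comparison can never mean anything.** It is undistorted in this way when treatment does not affect survival. It could be given a meaning under principal-stratum assumptions, but none are stated.
- **That graduation decisions are at risk.** The triggers rest on the primary POR alone. Length of stay has no decision rule, and no health-economic analysis is specified.

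The wording should be changed, but the main design does not depend on it.

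**What to change.** In section 9.6, replace the survivor population for length of stay with all randomised participants for the inferential analysis, by one of two routes:

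- ICU-free and hospital-free days to day 90, with death as the worst category, in the primary's ordinal model; or
- time to discharge alive from ICU and from hospital, with death as a competing event.

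Keep survivors' length of stay as a descriptive summary by arm, and state the survival horizon that defines a survivor. Carry the same wording into the SAP.

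The cost is protocol and SAP text and a little analysis. The visit schedule (section 6.4) already collects ICU and hospital data up to day 90, and section 9.6 already applies the primary's model to the support-free-day endpoints. The price in interpretation is that mean days in survivors is no longer the inferential summary, and that the new measure partly reflects mortality and so overlaps with endpoints already reported.
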